NON-INTERVENTIONAL (NI) STUDY PROTOCOL

Study information

Title	Patient outcomes and clinical characteristics of ATTR-CM patients treated with tafamidis: A single center experience in Turkey- Study ATTREAL
Protocol number	B3461126
Protocol version identifier	2.0
Date	16 December 2025
EU Post Authorization Study (PAS) register number	EUPAS1000000561
Active substance	N07XX08
Medicinal product	Tafamidis
Research question and objectives	
The aim of this study is to describe the clinical characteristics and outcomes of patients with ATTR amyloid cardiomyopathy (ATTR-CM) treated with tafamidis at a single center in Turkey.
 
Primary Objective:
 
To describe the rate of hospitalizations and emergency admissions due to chronic heart failure in the patients treated with Tafamidis
 
Secondary Objectives:
 
- To describe the rate of cardiovascular-related hospitalizations and overall survival among patients treated with Tafamidis during Tafamidis exposure time period.- To describe the presence of cardiac and extracardiac red flags (Extra-cardiac Red Flags: Carpal Tunnel Syndrome, Peripheral Neuropathy, Lumbar Stenosis, Renal Insufficiency, Cardiac Red Flags: Elevated NT Pro BNP and troponin, Pseudo infarct Sign, Voltage Mismatch, Conduction Disorder, Increased Wall Thickness (Interventricular septum), Pericardial Effusion)) in patients with ATTR - CM treated with tafamidis during the baseline period prior to initiation of tafamidis treatment.

	
- To describe the clinical and functional outcomes in ATTR CM patients during the baseline period prior to tafamidis treatment and during the follow-up period of treatment with tafamidis such as HRQoL (Health-Related Quality of Life) measures, concomitant medication, biomarkers (NT pro-BNP, troponin), echocardiographic parameters (6 min walk test, Kansas City Cardiomyopathy Questionnaire Score, Creatinine eGFR, Ejection Fraction, Interventricular Septum, E/A ratio, E/e' mean ratio, Tricuspid Regurgitation Velocity, Tricuspid Annular Plane Systolic Excursion).

Country(ies) of study	Turkey
Author	[name], ████████████████████ ████████████████████ ████████████████████

1. LIST OF ABBREVIATIONS

Abbreviation	Definition
AEM	Adverse Event Management
AL	Amyloid Light Chain (other type of amyloidosis to differentiate from ATTR)
ALT	Alanine Transaminase
AF	Atrial Fibrillation
AST	Aspartate Aminotransferase
ATTR-ACT	TTR Amyloidosis Cardiomyopathy Clinical Trial
ATTR CM	TTR amyloid cardiomyopathy
AV	Atrioventricular
BMI	Body Mass Index
BPM	Beats Per Minute
CA	Cardiac Amyloidosis
CIOMS	Council for International Organizations of Medical Sciences
CSA	Clinical Study Agreement
CHF	Chronic Heart Failure
eCRF	Electronic Case Report Form
CRO	Clinical Research Organization
COPD	Chronic Obstructive Pulmonary Disease
CV	Cardiovascular
E/A Ratio	Early to Atrial filling velocity ratio
EC	Ethics Committee
ECG	Electrocardiogram
ECHO	Echocardiography
EDP	Exposure during pregnancy
eGFR	Estimated Glomerular Filtration Rate
E/e' ²	Early mitral inflow velocity and mitral annular early diastolic velocity ration
EF	Ejection Fraction
EHR	Electronic Health Record
EMA	European Medicines Agency
ENCepp	European Network of Centres for Pharmacoepidemiology and Pharmacovigilance
FDA	Food and Drug Administration
GPP	Good Pharmacoepidemiology Practices
HF	Heart Failure (symptom management focus)
HFpEF	Heart Failure with Preserved Ejection Fraction
HFmrEF	Heart Failure with mildly reduced ejection fraction
HFrEF	Heart Failure with reduced ejection fraction
HRoL	Health-Related Quality of Life
hATTR	Hereditary TTR Amyloidosis
ICD	International Classification of Diseases

ICMJE	International Committee of Medical Journal Editors (ICMJE)
IRB	Institutional Review Board
ISPOR-ISPE	International Society for Pharmacoeconomics and Outcomes Research - International Society for Pharmaceutical Engineering
IVS	Interventricular Septum
KCCQ	Kansas City Cardiomyopathy Questionnaire
LAVI	Left Atrial Volume Index
LVMi	Left Ventricular Mass Index
LVEDD	Left Ventricular End-Diastolic Dimension
LVEDSD	Left Ventricular End-Systolic Dimension
MRI	Magnetic Resonance Imaging
NIS	Non-interventional study
NT-proBNP	N-terminal pro-B-type Natriuretic Peptide
NYHA class	The NYHA (New York Heart Association) Functional Classification
PW	Posterior Wall
RWD	Real World Data
PYP/ DPD/ HMDDP	Pyrophosphate / Diphosphono-1,2-propanodicarboxylic acid / Hydroxymethylene Diphosphonat
RBP	Retinol-binding protein
RWE	Real-World Evidence
AEs/SAEs	Adverse Events (AEs) and Serious Adverse Events (SAEs)
SAP	Statistical Analysis Plan
SAVR	Surgical Aortic Valve Replacement
SOP	Standard Operating Procedures
sPAP	Systolic Pulmonary Artery Pressure
SPECT-CT	Single-Photon Emission Computed Tomography
T4	Thyroxine
T60A	Genetic mutation where the amino acid threonine (T) at position 60 of a protein is replaced by alanine (A)
TAPSE	Tricuspid Annular Plane Systolic Excursion
TAVI	Transcatheter Aortic Valve Implantation
TTR	Transthyretin (protein involved in amyloidosis)
TTR Stabilizers	Transthyretin Stabilizers
V122I	Genetic mutation where amino acid valine (V) is substituted by isoleucine (I) at position 122
wtATTR	Wild-Type TTR Amyloidosis
YRR	Your Reporting Responsibilities
6MWT	6-Minute Walk Test
99mTc	Technetium-99m (used in imaging studies)

3. ABSTRACT

Title: Patient outcomes and clinical characteristics of ATTR-CM patients treated with tafamidis: A single center experience in Turkey

Version 1.0, 16 December 2025

[name], [REDACTED]

Rationale and background: ATTR-CM is an advanced and complicated disease caused by the aggregation of misfolded TTR proteins in the heart, resulting in restrictive cardiomyopathy and heart failure. Tafamidis, an FDA approved agent, TTR stabilizer, has been studied for its potential to modify the disease and improve clinical outcomes in patients with wild-type or variant transthyretin amyloidosis. Although tafamidis has changed the treatment algorithm, patient outcomes and clinical characteristics in the real-world settings, especially in populations with unique genetic, clinical, and healthcare system characteristics such as Turkey is poorly understood. Regional differences in genetic mutations, access to advanced diagnostic tools, and healthcare practices may influence patient outcomes. Tafamidis is currently the only approved treatment option for ATTR-CM, it is approved and reimbursed for patients in Turkey.

This study represents the first comprehensive descriptive study of patient outcomes following tafamidis treatment in Turkey. The findings will enhance understanding of ATTR-CM epidemiology and serve as a valuable resource for improving disease awareness among cardiologists and shaping future diagnostic and therapeutic guidelines.

Research question and objectives: The aim of this study is to describe the clinical characteristics and outcomes of patients with ATTR amyloid cardiomyopathy (ATTR-CM) treated with tafamidis at a single center in Turkey.

Primary Objective: to describe the rate of hospitalizations and emergency admissions due to chronic heart failure in the patients treated with Tafamidis.

Secondary Objectives:

- To describe the rate of cardiovascular-related hospitalizations and overall survival among patients treated with Tafamidis during Tafamidis exposure time period.
- To describe the presence of cardiac and extracardiac red flags (Extra-cardiac Red Flags: Carpal Tunnel Syndrome, Peripheral Neuropathy, Lumbar Stenosis, Renal Insufficiency, Cardiac Red Flags: Elevated NT Pro BNP and troponin, Pseudo infarct Sign, Voltage Mismatch, Conduction Disorder, Increased Wall Thickness (Interventricular septum), Pericardial Effusion)) in patients with ATTR - CM treated with tafamidis during the baseline period prior to initiation of tafamidis treatment.
- To describe the clinical and functional outcomes in ATTR CM patients during the baseline period prior to tafamidis treatment and during the follow-up period of treatment with tafamidis such as HRQL (Health-Related Quality of Life) measures, concomitant medication, biomarkers (NT pro-BNP, troponin), echocardiographic parameters (6 min walk test, Kansas City Cardiomyopathy Questionnaire Score, Creatinine eGFR, Ejection Fraction, Interventricular Septum, E/A ratio, E/e' mean ratio, Tricuspid Regurgitation Velocity, Tricuspid Annular Plane Systolic Excursion).

Study design: This is a single-center, non-interventional, retrospective cohort study.

PFIZER CONFIDENTIAL

Population: Patients must meet the following inclusion criteria: 1) >18 years old at the time of diagnosis; ii) diagnosed with hereditary or wild type ATTR-CM confirmed non-invasively (Tc99m PYP bone scintigraphy and/or SPECT-CT) in Samsun Education and Research Hospital – Cardiology Outpatient Clinic between January 2023 – January 2025; iii) currently receiving or who have received tafamidis treatment for ATTR-CM; iv) Availability of complete medical records, including baseline clinical characteristics, treatment outcomes, and follow-up data from electronic health record systems of hospital or physical patient files. Patients will be excluded if participated in studies involving investigational drugs within 24 months before the index date.

Variables: Demographics, NYHA class, 6-minute walk test (6MWT), quality of life, Electrocardiogram (ECG), echocardiography, and Magnetic Resonance Imaging (MRI) data, blood parameters, including troponin and N-terminal pro Brain Natriuretic Peptide (NT pro-BNP), Estimated Glomerular Filtration Rate (eGFR) Biomarkers, Bone scintigraphy/SPECT Imaging, Genetic tests, Serum protein electrophoresis, Serum/urine immunofixation electrophoresis

Data source: Pseudonymized data will be entered in CRF from individual patient medical records maintained in a single center in Turkey according to clinical practice. Data will be collected using electronic case report form (eCRF).

Sample size: Due to the absence of a priori hypothesis, sample size calculations are not applicable, and no formal sample size calculation has been performed. According to the descriptive nature of the study, we have planned a sample of around 70 subjects approximating 10% of the entire population diagnosed with ATTR-CM in Turkey, with no formal calculation related to a specific endpoint.

Data analysis: Descriptive statistics will be reported and no effort to determine statistical significance will be made.

Milestones:

Milestone	Planned Date
Registration in the HMA-EMA Catalogues of RWD studies	30 July 2025
Start of data collection	16 October 2025
End of data collection	30 June 2026
Final study report	31 December 2026

4. AMENDMENTS AND UPDATES

Version Identifier	Date	Amendment Type (substantial or administrative)	Protocol Section(s) Changed	Summary of Amendment(s)	Reason				
2.0	16 Dec 2025	Substantial	5. Milestones	Start of data collection, end of data collection, and final study report dates are postponed per the actual data collection start date.	Completion of site agreement and therefore the SIV were completed later than initially planned. Due to these, data collection has started later than initially planned and actual data collection start date is mentioned in the revised version. Due to the increase in subject number, longer duration is now anticipated for completion of data entry. Therefore, dates of end of data collection and final study report are also postponed accordingly.				
						Substantial	3. Abstract	Sample size is increased to 70.	Since the start of data collection is postponed, number of eligible patients at the study site has increased during that duration. To obtain more comprehensive data, it is decided to include all eligible patients to the study.
						Substantial	8.5. Study Size		
						Substantial	3. Abstract		
						Substantial	8.2. Setting		
						Administrative	8.3. Variables		
Administrative	8.3. Variables	Assessment period of the variable “NYHA Class” is corrected to include the “follow-up	Due to an error and oversight, “follow-up assessment period” of the “NYHA Class” was initially omitted and now updated accordingly.						

Version Identifier	Date	Amendment Type (substantial or administrative)	Protocol Section(s) Changed	Summary of Amendment(s)	Reason
		Administrative	8.3. Variables	Operational definition of the variable "Carpal Tunnel Syndrome" is changed to "History of Carpal Tunnel Syndrome (yes/no/missing) as documented in the source data".	Due to an error and oversight, operational definition of the "Carpal Tunnel Syndrome" was initially mentioned incorrectly and now updated accordingly.
		Administrative	8.3. Variables	Variable name "Tafamidis treatment start date" is changed to "Tafamidis treatment prescription date".	Due to an error and oversight, variable name and operational definition of the "Tafamidis treatment prescription date" were initially mentioned incorrectly and now updated accordingly.
		Administrative	Secondary Objective	Patients' follow-up period is clarified.	Since the follow-up duration of the patients will change (approximately min. 6 months to max. 30 months) depending on the Tafamidis exposure time period, the duration of follow-up period of approximately 12 months was removed from the formulation of the secondary objective.

Version Identifier	Date	Amendment Type (substantial or administrative)	Protocol Section(s) Changed	Summary of Amendment(s)	Reason
		Administrative	8.2. Setting	Cut-off/end of the patients' follow-up period is clarified.	Study team decided to clarify the cut-off/end of the patients' follow-up period and the relevant paragraph is included in the 8.2 Setting section.
		Administrative	8.6. Data Management	Cut-off/end of the patients' follow-up period is clarified.	"Data Collection and Entry" section of the 8.6. Data Management is revised to reflect the current data collection period.
		Administrative	8.3. Variables	Units of sodium, potassium, albumin, NT pro-BNP, and serum free light chain levels (kappa and lambda) are changed.	Units of some laboratory parameters are changed to align with the actual units implemented by the site.
		Administrative	Overall	Minor clerical errors were corrected.	

5. MILESTONES

Milestone	Planned Date
Registration in the HMA-EMA Catalogues of RWD studies	30 July 2025
Start of data collection	16 October 2025
End of data collection	30 June 2026
Final study report	31 December 2026

6. RATIONALE AND BACKGROUND

Amyloidosis is a systemic disorder characterized by the abnormal extracellular deposition of misfolded proteins, which aggregate into amyloid fibrils. These fibrils can deposit in various tissues and organs, impairing their normal function. The two most common forms of cardiac amyloidosis are AL amyloidosis and ATTR amyloidosis, each caused by different proteins.¹⁻³

ATTR amyloidosis involves the deposition of misfolded TTR, a protein primarily produced by the liver. ATTR amyloidosis can be hereditary or wild type. Hereditary ATTR amyloidosis (hATTR) is associated with mutations in the TTR gene, while wild-type ATTR (wtATTR) occurs due to aging and is more common in older individuals.²⁻³

Treatment strategies aim to reduce amyloid deposition and manage the associated heart failure symptoms. In ATTR amyloidosis, tafamidis has shown efficacy in reducing disease progression and improving clinical outcomes, including heart-related symptoms.⁴

Cardiac amyloidosis is characterized by the extracellular accumulation of abnormal proteins. Regardless of the subtype of the deposited amyloid, the disease results in progressive heart failure if left untreated. TTR is a tetrameric transport protein primarily synthesized in the liver, responsible for carrying T4 and RBP. Under pathological conditions, TTR dissociates into monomers, which misfold and aggregate into insoluble amyloid fibrils. These fibrils infiltrate the cardiac interstitium, causing myocardial stiffening, diastolic dysfunction, and eventually heart failure.⁵

1. **wtATTR:** Studies show that approximately 25% of individuals over 80 years have cardiac amyloid deposits.⁶ Occurs due to age-related destabilization of TTR, typically presenting after the age of 60–65 years. More prevalent in men and often associated with carpal tunnel syndrome and spinal stenosis as early non-cardiac manifestations. Historically underdiagnosed but increasingly recognized with advancements in imaging techniques.⁷

2. **hATTR:** The prevalence is influenced by regional genetic factors. Caused by autosomal dominant mutations in the TTR gene. Over 120 mutations have been identified, with the most common being V122I (3-4% of African Americans) and T60A (Northern Europe).^{8,9}

Patients with ATTR-CM typically present with symptoms of heart failure, including dyspnea, fatigue, and peripheral edema. Key distinguishing features include:

Hussain K et al. evaluated the impact of tafamidis on overall survival in patients with ATTR-CM within a community-based cohort in a retrospective observational study analyzing patient data from a community hospital comparable to the current setting. The study supports the efficacy of tafamidis observed in clinical trials, indicating its beneficial impact extends to routine clinical practice.¹⁸ Additionally, in an Egyptian study claims that the variability in patient response emphasizes the need for individualized treatment approaches. Ongoing research and long-term studies are essential to fully understand the benefits and limitations of tafamidis therapy in diverse patient populations.¹⁹

Emerging Therapies

Recent developments in the treatment landscape for ATTR-CM include the FDA/EMA approvals of new therapies worldwide such as acoramidis (Atruby) by BridgeBio and positive trial results for vutrisiran by Alnylam Pharmaceuticals. These advancements indicate a growing array of therapeutic options for patients with ATTR-CM.²⁰

Rationale

While several advancements have been made in diagnosing and treating ATTR-CM, gaps in knowledge still remain.

[REDACTED]

The disease may present with variable presentations based on genetic and non-genetic forms (wild-type vs. hereditary). Understanding the mechanisms driving this heterogeneity remains still incomplete. While tools like bone scintigraphy and cardiac MRI have improved diagnostic options, there is limited standardization of non-invasive diagnostic criteria and biomarkers for early disease detection. ATTR-CM remains underdiagnosed due to its nonspecific symptoms that overlap with other forms of heart failure and cardiomyopathies. The lack of awareness among cardiologists often results in delayed or missed diagnoses. Therefore, our study aims to address these gaps by providing comprehensive real-world data on Turkish patients with ATTR-CM treated with tafamidis.

This noninterventional study is designated as a PASS and is conducted voluntarily by Pfizer.

7. RESEARCH QUESTION AND OBJECTIVES

The aim of this study is to describe the clinical characteristics and outcomes of patients with ATTR amyloidoid cardiomyopathy (ATTR-CM) treated with tafamidis at a single center in Turkey.

Primary Objective:

- To describe the rate of hospitalizations and emergency admissions due to chronic heart failure in the patients treated with Tafamidis

Secondary Objectives:

- To describe the rate of cardiovascular-related hospitalizations and overall survival among patients treated with Tafamidis during Tafamidis exposure time period.
- To describe the presence of cardiac and extracardiac red flags (Extra-cardiac Red Flags: Carpal Tunnel Syndrome, Peripheral Neuropathy, Lumbar Stenosis, Renal Insufficiency, Cardiac Red

Flags: Elevated NT Pro BNP and troponin, Pseudo infarct Sign, Voltage Mismatch, Conduction Disorder, Increased Wall Thickness (Interventricular septum), Pericardial Effusion)) in patients with ATTR - CM treated with tafamidis during the baseline period prior to initiation of tafamidis treatment.

- To describe the clinical and functional outcomes in ATTR CM patients during the baseline period prior to tafamidis treatment and during the follow-up period of treatment with tafamidis such as HRQoL measures, concomitant medication, biomarkers (NT pro-BNP, troponin), echocardiographic parameters (6 min walk test, Kansas City Cardiomyopathy Questionnaire Score, Creatinine eGFR, Ejection Fraction, Interventricular Septum, E/A ratio, E/e' mean ratio, Tricuspid Regurgitation Velocity, Tricuspid Annular Plane Systolic Excursion).

8. RESEARCH METHODS

8.1. Study Design

This is a single-center, retrospective, non-interventional cohort (Figure 1) study. Pseudonymized data will be entered in CRF from individual patient medical records maintained in a single center in Turkey according to clinical practice. Data will be collected using electronic case report form (eCRF). Subjects include diagnosed with ATTR-CM in the January 2023 – January 2025 and treated with tafamidis. For all patients, the 6-month period before the index date when tafamidis is started will be considered as the baseline period, and the relevant parameters will be collected from this period. From the start of tafamidis, quarterly follow up of the patients is defined as treatment period and clinical and functional outcomes, hospitalization and emergency admission due to CHF, CV related hospitalizations and mortality data will be obtained from this treatment period. Tafamidis treatment discontinuation is defined as interrupting the treatment for at least 10 days or completely stopping it, which will be determined by the primary investigator from the EHR records (Electronic Health Record). Hospitalization and emergency admission due to CHF (Chronic Heart Failure) and CV (Cardiovascular) related hospitalizations and other variables are described in Section 9.3.1. and Table 1.

[figure not shown]

Figure 1. Study diagram

Rationale for the study design. The rationale for choosing a retrospective cohort design is that the data points of interest outlined in the study protocol are routinely collected in the Turkish clinical practice. Therefore, the retrospective approach will ensure that the dataset is available on the site. The single center participating in the study is highly specialized and skilled in the management of the target population.

This study is a cohort study because it involves following a group of ATTR CM patients who share common characteristics (in this case, the target population managed by the specialized center) over a period. Since the ATTR CM is a progressive disease, a cohort design will allow longitudinal evaluation of clinical outcomes and progression as managed in real world clinical practice. The cohort design was chosen instead of different study designs because it allows for the longitudinal evaluation of clinical outcomes and disease progression in patients with ATTR amyloid cardiomyopathy (ATTR-CM), which is essential for understanding the impact of tafamidis treatment over time. This design leverages routinely collected data in Turkish clinical practice, ensuring the availability of relevant information and reflecting real-world settings. Additionally, the specialized center's expertise in managing ATTR-CM patients enhances the reliability and applicability of the study results.

Strength of the study is described in the [Section 9.7](#) (Strengths and Limitations of the Research Methods).

8.2. Setting

One Turkish Centre involved in the diagnosis and management of patients affected by ATTR-CM will participate in the study. This Centre is selected according to their clinical and research expertise, in

addition to the number of patients they are used to routinely caring for. A clinical research organization (CRO) on behalf of Pfizer will support the regulatory and administrative procedures to get authorization and the operations at Centre needed for data collection.

After regulatory authorization and local contract finalization, the study will be started at Centre. The site Study Team, including the Principal Investigator and additional identified personnel (e.g., research nurse, clinical study manager) will be trained on the protocol and planned study procedures, in addition to the use of the study-specific eCRF. Study data will be collected according to [Section 9.1. Study Design](#) and [Figure 1](#) as patients are diagnosed with ATTR-CM between January 2023 and January 2025. For all patients, the 6-month period before the index date when tafamidis is started will be considered as the baseline period, and the relevant parameters will be collected from this period. Original data, routinely collected by means of specific tools (e.g., paper charts, electronic charts,) will be transferred to the eCRF by the Study Team in site.

Retrospective data from the patient's files/source data will be collected in the CRF up to the earliest date of: treatment discontinuation, death, lost to follow-up (the patient could not be observed and any more contacted at some time point during their follow-up) or end of the follow-up period of 30-Sep-2025 (inclusive). For the patients lost to follow-up, the end of their follow-up period will be the respective date of the last contact. In the case patients experience clinical events (e.g. hospitalization due to Chronic Heart Failure, safety event) starting before 30-Sep-2025 and continuing beyond end of the follow-up, the respective details until the end of the event should be included into the eCRF.

The CRO will ensure oversight and monitoring of the study at the site.

Approximately seventy (70) subjects who meet the inclusion and exclusion criteria detailed below will be included in the study. The inclusion and exclusion criteria were established based on the diagnosis of ATTR-CM disease and the evaluation of tafamidis treatment outcomes as outlined in the study objectives. The study population formed in light of these criteria is expected to represent the source population and the population of Turkey.

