8.2.1. Inclusion Criteria

Patients must meet all the following inclusion criteria to be eligible for inclusion in the study:

1. ≥ 18 years old at the time of diagnosis of ATTR-CM,
2. Diagnosed with hereditary or wild type ATTR-CM confirmed non-invasively (Tc99m PYP bone scintigraphy and/or SPECT-CT) in Samsun Education and Research Hospital – Cardiology Outpatient Clinic between 1 January 2023 – 1 January 2025,
3. Currently receiving or who have received tafamidis treatment for ATTR-CM,
4. Availability of complete medical records, including baseline clinical characteristics, treatment outcomes, and follow-up data from electronic health record systems of hospital or physical patient files.

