Pericardial Effusion	Cardiac Red Flags, Secondary Objective	Baseline Assessment Period	Nominal	Electronic health records or physical patient file	Accumulation of fluid in the pericardial sac exceeding the physiological amount (present: Yes; or not: No)
Biatrial Dilatation	Patient Baseline Echo Parameters, Secondary Objective	Baseline Assessment Period	Nominal	Electronic health records or physical patient file	Enlargement of both atria, (present: Yes; or not: No)
Valve Thickening	Cardiac Red Flags, Secondary objective	Baseline Assessment Period	Nominal	Electronic health records or physical patient file	Increased thickness of heart valves, assessed via echocardiography (present: Yes; or not: No)
Tc99m PYP uptake; Perugini score	Patient Baseline Clinical Parameters,	Baseline Assessment Period	Ordinal	Electronic health records or physical patient file	Semi-quantitative visual scoring system for Tc99m PYP uptake, used

(PYP cardiac Scintigraphy Grade)	Secondary objective				to differentiate cardiac ATTR from AL amyloidosis (Grade 0-1-2-3)
Identification of hereditary vs. wild-type ATTR-CM (Wild - Variant)	Patient Baseline Clinical Parameters, Secondary objective	Baseline Assessment Period	Nominal	Electronic health records or physical patient file	Wild and Variant type of ATTR CM, this variable is defined by the TTR mutation test result, as recorded in the source data
TTR mutation variant (V30M, V122I, T60A, Ala81Thr, Arg34Gly, Other)	Patient Baseline Clinical Parameters, Secondary objective	Baseline Assessment Period	Nominal	Electronic health records or physical patient file	Mutation Type: V30M, V122I, T60A, Ala81Thr, Arg34Gly and other
6 min walking test m	Functional outcome, Secondary objective	Index, Follow up Assessment Period	Continuous	Electronic health records or physical patient file	Tests results as recorded in the source data
KCCQ Score per treatment (Kansas City Cardiomyopathy Questionnaire)	Functional outcome, Secondary objective	Index, Follow up Assessment Period	Ordinal	Electronic health records or physical patient file	Assessing physical limitations, symptoms, self-efficacy, social interference, and quality of life in heart failure patients.

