8.6. Data Management

Data management will be performed by the CRO acting on behalf of Pfizer.

Data Collection and Entry: Patient data will be collected retrospectively from electronic health record systems maintained at the single participating center. The treatment protocol notes data will be collected in the eCRF. The data collection period is between January 2023 and September 2025. Patient data will be collected during the baseline diagnosis period and then throughout the treatment period (while the patient is under tafamidis treatment) during follow-ups period. The study does not involve any patient contact and will not impact the care patients receive. Preidentified data regarding the patients will be collected in electronic Case Report Forms eCRF and analyzed to accomplish the proposed study objectives.

Data will be collected on the e-CRF application, which will be prepared based on the CRF that will be developed specifically for this study. The e-CRF will meet the scientific, regulatory, and logistical requirements of the study before it is used to record data for this study. Before using the e-CRF, all users will receive training on the system and study specific training.

The single investigator from a single center and a site coordinator will be defined in the system. Form controls will be used for the appropriate data fields (for data fields with clear boundaries and content), this will prevent any data entry outside the limits set for the investigator. For data fields that cannot be limited by form controls but have boundaries, automatic form controls will be provided in the system.

All data required for the study, including nurses' measurements, patient demographics and necessary previous medical records will be recorded to the e-CRF manually by the investigator. The investigator is responsible for the accuracy of these manually recorded data.

During patient data entry, the faulty/missing data scan will be performed by the e-CRF automatically. In this way, any form with faulty or missing data will not be allowed to send data to e-CRF, and warning messages will be displayed on the computer screen to the person entering the data to ensure that he/she enter data correctly and completely.

Data cleaning and, if necessary, source data verification will be conducted. After cleaning, the database will be locked, and the data will be extracted in the appropriate format.

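### The 6-month pre-index baseline conflicts with a data period that starts in January 2023, and it is also applied to one-off diagnostic tests with no look-back of their own

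*Protocol*

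**What the plan says.** Protocol 8.1 and 8.2 fix the baseline for all patients: "the 6-month period before the index date when tafamidis is started will be considered as the baseline period".

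Protocol 8.6 gives the calendar span of the data: "The data collection period is between January 2023 and September 2025". The same section adds: "Patient data will be collected during the baseline diagnosis period and then throughout the treatment period". Its term for baseline differs from the one in 8.1 and 8.2 and is not defined.

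The inclusion criteria (8.2.1) date the diagnosis, "between 1 January 2023 – 1 January 2025", and require treatment only in these terms: "Currently receiving or who have received tafamidis treatment for ATTR-CM". They set no maximum interval between the two.

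Table 1 (8.3) places serum free light chains, immunofixation, Perugini grade, wild-type or variant status and the TTR variant in the Baseline Assessment Period. For wild-type or variant status it says "this variable is defined by the TTR mutation test result, as recorded in the source data". Where a patient has several baseline measurements, 8.3 takes the one nearest to index. It has no rule for a result dated before the window. Section 8.7 rules out imputation.

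**The concern.** There are two separate problems.

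First, an abstractor cannot follow both 8.2 and 8.6 for a patient who starts tafamidis before July 2023. One section asks for six months of look-back, and the other stops at January 2023.

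Second, a diagnostic work-up is done around diagnosis, whereas the window is anchored to treatment start. If treatment starts more than six months after the work-up, the results fall outside the only period Table 1 allows for them, even though a genotype does not change.

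At stake are the completeness and consistency of the baseline description, which serves secondary objectives. A result that is in the chart could be entered as missing for one patient and recorded for another, depending on how staff read the rule.

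**Working it through.** **Inputs.** Diagnosis 1 January 2023 to 1 January 2025 (8.2.1); end of follow-up 30 September 2025 (8.2); baseline 6 months before index (8.1, 8.2); data from January 2023 (8.6); about 70 patients (8.2). The protocol does not give the diagnosis-to-index gap, so it is assumed below. Index is taken to be on or after diagnosis. One month = 30.4375 days.

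**1. The protocol's own related figure.** The only figure that bears on the gap is a follow-up of about 6 to 30 months, in the reason column of the amendment table (Section 4).
- Earliest diagnosis to end of follow-up: 1003 days / 30.4375 = 32.95 months.
- Latest diagnosis to end of follow-up: 272 / 30.4375 = 8.94 months.
- With a gap of 3 months: 32.95 − 3 = 29.95 and 8.94 − 3 = 5.94.

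Both ends are reproduced by a gap of about 3 months. The range limits index dates, however, and not individual gaps. A patient diagnosed on 1 January 2023 and treated from 31 March 2025 still has 6 months of follow-up, with a gap of 820 / 30.4375 = 26.9 months.

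**2. Date conflict.** The window starts at index minus 6 months. It starts before 1 January 2023 whenever index is before 1 July 2023. At a 3-month gap the earliest index is about 1 April 2023, and its window opens about 1 October 2022.

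With diagnoses uniform over 24 months and a fixed gap g, the share with a truncated window is (6 − g) / 24 for g up to 6:

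| Gap g (months) | Share | Of 70 |
|---|---|---|
| 0 | 6/24 = 25% | 17.5 |
| 3 | 3/24 = 12.5% | 8.75 |
| 6 | 0/24 = 0% | 0 |

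**3. Work-up outside the window.** Taking the work-up at the diagnosis date, it is outside when the gap exceeds 6 months. For an exponential gap with mean m, the share is exp(−6/m), slightly less once index is required to fall before month 33. Simulation with that restriction (one million draws per mean):

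| Mean gap (months) | Share with gap over 6 months | Of 70 |
|---|---|---|
| 1 | 0.3% | 0.2 |
| 2 | 4.9% | 3.4 |
| 3 | 13.0% | 9.1 |
| 4 | 20.9% | 14.7 |
| 6 | 33.1% | 23.2 |

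Longer delays push the share higher: an exponential median of 6 months gives 43%. If every patient had a gap of about 3 months, the share would be zero.

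**4. Overlap.** Diagnosis is on or after 1 January 2023, so a gap above 6 months puts index after 1 July 2023, where the window is no longer truncated. Measured from the diagnosis date, no patient has both problems. The simulation counted none.

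**The case against.** The strongest reply is that nothing need be lost. No section tells staff to discard an older result. Genotype is taken as recorded in the source, and 8.6 speaks of a diagnostic baseline, which suggests that the work-up is meant to be collected. The stated follow-up range fits a typical gap of about 3 months, at which the work-up falls inside the window. Figure 1 is not available here and may bear on the windows. Most of this stands, and it is why the point is about possible omission and inconsistent handling. It does not remove the conflict: a second, undefined baseline term adds an ambiguity, and the follow-up range is approximate and sets no cap on the gap.

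It might also be said that the period in 8.6 describes when the abstraction takes place. Section 5 dates the abstraction from 16 October 2025 to 30 June 2026, so the 8.6 period can only be the span of the data themselves.

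Several stronger readings are tempting and are not supported:
- *The January 2023 start loses the scintigraphy grade.* The confirming scan dates the diagnosis, which must be on or after 1 January 2023. Only light-chain or genetic tests done before diagnosis, and earlier time-varying measures, are exposed.
- *A truncated window means lost values.* Section 8.3 records the measurement nearest to index, so a value is lost only if nothing was measured between January 2023 and index. The shares in step 2 should not be added to those in step 3 as patients with missing data.
- *Patients will be excluded.* Criterion 4 asks for "Availability of complete medical records, including baseline clinical characteristics, treatment outcomes, and follow-up data". That concerns the availability of records, not a value for every variable within the window, and 8.7 and 8.9 expect some missing items.
- *Comorbidities and history-type red flags are affected.* Most are already defined as history documented in the source, so the 6-month limit hardly touches them.

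**Conclusion.** Two defects stand.

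The conflict between 8.1/8.2 and 8.6 is certain on the text for any index before 1 July 2023. Its reach is about 25% of windows at zero gap, 12.5% at 3 months and none at 6 months, assuming evenly spread diagnoses. These are truncated windows, and the share with values actually missing cannot be derived from the protocol.

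The tie of one-off diagnostic tests to the 6-month window is a design weakness of unknown size: about 0% to 33% of patients for assumed exponential mean gaps of 1 to 6 months, and none if gaps are uniformly about 3 months. A reader might infer that genotype, scintigraphy and light-chain results will be lost for part of the cohort. The protocol supports only that they may be unrecorded or inconsistently handled, because this needs both a gap above 6 months and a strict reading of the window.

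Neither defect affects the primary outcome, which uses follow-up events only. The correction is worth making because it is specific and cheap, and chart abstraction is planned to run until 30 June 2026.

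**What to change.** - **Table 1 (8.3):** for genotype, Perugini grade, free light chains and immunofixation, take the latest record at any time up to index, exempt from the January 2023 start, and show the test date relative to index.
- **Time-varying measures** (routine laboratory values, ECG, echo, NYHA class): keep the 6-month window.
- **8.6:** start the data-collection period in July 2022, or define it as 6 months before each patient's index, and use the same baseline term as 8.1 and 8.2.
- **Reporting:** describe the time from diagnosis to index, so that readers can see how many patients started more than 6 months after diagnosis.

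The cost is wording in Table 1 and 8.6, plus a few extra dates and results from charts already under review. The small downside is that some diagnostic results will be older than 6 months, which the reported test date makes visible.
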